6.7 BASELINE, TIME WINDOWS AND CALCULATED VISITS

Study days and visits will be labelled according to the flowchart in the CTP.

Unless otherwise specified baseline is defined as the time point closest to but prior to the first administration of any study medication. If no time is specified and the date is the same as the first administration date, then it will still be considered baseline if not specified otherwise. If there is no measurement earlier than the first administration of study medication, then no baseline will be derived.

Laboratory values:

Baseline is defined as the latest time point before the very first administration of any study medication. For laboratories where not only the examination date but also time are recorded, examination time has to be taken into account when defining baseline. That is, a laboratory value on the same date as the first administration of study medication is considered as baseline value if and only if the time of laboratory assessment is before or the same as the time of first study drug administration.

If any of these times is missing and the date of laboratory assessment is equal to the date of first administration of study medication, then the laboratory assessment will be considered as according to protocol, i.e. as prior to first study medication.

Imaging time windows:

In order to identify whether consecutive imaging time points are missing for a given patient, a nominal time point (6, 12, ... weeks etc.) will be assigned to each and every image. This is achieved by creating windows for every radiological response assessment. These windows are defined in Table 6.7: 1.

Table 6.7: 1 Nominal time points and windows for imaging

Nominal time point (weeks from start of study medication)	Due date of scans (days)*	Window (days)
6	43	1 to ≤ 64
12	85	65 to ≤ 106
18	127	107 to ≤ 148
24	169	149 to ≤ 200
33	232	201 to ≤ 263
42	295	264 to ≤ 326
51	358	327 to ≤ 389
Etc., 9 week interval	Etc.	Etc.

* the date of the first dose of study medication is Day 1

If a patient does not have an image in one of the windows described above, he/she will be said to have missed an assessment for that time point.

ECG analysis:

Baseline values will be derived from the 1-3 triplicate ECG recordings prior to the first drug administration on Day 1 (refer to [Section 7.8.4](#)).

7. PLANNED ANALYSIS

The labelling and display format of statistical parameters will follow the BI guideline (8).

All analyses are presented separately for the 3 trial parts, if not specified otherwise. Efficacy data are presented by dose cohort for Parts A and B and in total for Part C. Displays of safety data will be presented by dose cohort and in total for Parts A and B and in total for Part C, if not specified otherwise.

For End-of-Text tables, the set of summary statistics is: N / Mean / standard deviation (StD) / Min / Median / Max.

For tables that are provided for endpoints with some extreme data median, quartiles and percentiles should be preferred to Mean, StD, Min and Max.

For time-to-event analysis tables the set of statistics is: number of patients [N(%)], number of patients with event [N(%)], <time to event> [months] followed by P25 (25th percentile), median, P75 (75th percentile) and number of patients censored [N(%)]. If not specified otherwise the duration as well as the time to event will be displayed in months.

Tabulations of frequencies for categorical data will include all possible categories and will display the number of observations in a category as well as the percentage (%) relative to the respective treatment group (unless otherwise specified all patients in the respective patient set whether they have non-missing values or not). Percentages will be rounded to one decimal place. The category missing will be displayed only if there are actually missing values. The denominator of the main categories is defined by the number of patients in the used patient set. The main categories define the denominators of the subcategories. Subcategories should be intended and “[N(%)” will be displayed only for the main category. If a table includes only categorical data, “[N(%)” is to be displayed in the column header.

Sort order for general categorical variables: If categories correspond to the collected categories on the eCRF and the table shells do not explicitly specify the ordering, the “default ordering” defined by the eCRF is to be used in such cases. If categories are derived, the ordering as specified in the table shell document should be used; in general ordinal data (e.g. categorised continuous data) are to be displayed in ascending order.

Abbreviations (e.g. Wors.) should not be displayed without any explanations. They will be either spelled out in the table or explained in footnotes (whatever is more reasonable from the programming point of view).

If applicable, conversion from days to weeks, months and years will be as follows:

- Weeks = Days / 7
- Months = (Days * 12) / 365.25
- Years = Days / 365.25

7.1 DEMOGRAPHIC AND OTHER BASELINE CHARACTERISTICS

Descriptive statistics are planned for demographic characteristics, disease history, prior therapies, medical history, alcohol and tobacco use, baseline eastern cooperative oncology group (ECOG) performance status, and baseline disease assessment.

7.2 CONCOMITANT DISEASES AND MEDICATION

Descriptive statistics are planned for this section of the report. Concomitant diseases will be coded similarly as adverse events based on the most current Medical Dictionary for Regulatory Activities (MedDRA) version. Concomitant therapies (CTs) will be coded according to World Health Organization Drug Dictionary (WHO DD). CTs will be classified according to the Anatomical Therapeutic Chemical (ATC) classification system. The third ATC level will be used to categorise CTs by therapy type. In situations where a medical product may be used for more than one equally important indication, there are often several classification alternatives. As appropriate, patients receiving CTs with more than one possible ATC level 3 category will be counted more than once. Footnotes will clarify this possible double counting in tables.

7.3 TREATMENT COMPLIANCE

Treatment compliance will be listed in the appendix of the CTR. In general, the amount of and time for which BI 891065 and BI 754091 are taken will be interpreted in light of treatment exposure, efficacy and safety. Refer to [Section 5.4.2](#) and [Section 7.7](#) for further details on exposure analysis.

7.4 PRIMARY ENDPOINT(S)

Part A:

The primary endpoints of Part A are the MTD of BI 891065 and the number of patients with DLTs in the first treatment cycle. The number of patients with DLTs at each dose level will be presented for the first cycle for the MTD evaluation set and for the whole on-treatment period for the treated set separately.

The MTD will be determined by the SRC using recommendations from a Bayesian logistic regression model (BLRM, see CTP Section 7 for details on the model and on the prior). BLRM evaluations for the CTR will be performed once using the number of patients with DLTs during the first cycle from the MTD evaluation set and once using the number of patients with DLTs during the whole on-treatment period from the treated set.

Tables and bar charts displaying the posterior probabilities of the true DLT rates being in either the underdosing interval, the targeted toxicity interval or the over toxicity interval will be produced.

Part B:

The primary endpoints of Part B are the MTD of BI 891065 in combination with BI 754091 and the number of patients with DLTs in the first treatment cycle. The number of patients

with DLTs at each dose level will be presented for the first cycle for the MTD evaluation set and for the whole on-treatment period for the treated set separately.

The MTD will be determined by the SRC using recommendations from a BLRM (see CTP Section 7 for details on the model, the prior for Part B is described in [Section 9.1](#) of this TSAP). BLRM evaluations for the CTR will be performed once using the number of patients with DLTs during the first cycle from the MTD evaluation set and once using the number of patients with DLTs during the whole on-treatment period from the treated set.

Tables and bar charts (per dose level of BI 754091) displaying the posterior probabilities of the true DLT rates being in either the underdosing interval, the targeted toxicity interval or the over toxicity interval will be produced.

Part C:

The primary endpoint of Part C is OR by investigator's assessment based on RECIST v1.1. OR will be analysed descriptively for the treated set in terms of objective response rate (ORR), defined as the proportion of patients with best overall response of CR or PR.

An interim futility analysis will be performed by the SRC after 20 patients have been treated for at least 18 weeks. Enrolment into Part C will be stopped if less than 2 patients with OR have been observed in these 20 patients. Results of this interim analysis will be documented in the SRC minutes.

7.5 SECONDARY ENDPOINT(S)

7.5.1 Key secondary endpoint(s)

Not applicable as no key secondary endpoints have been defined in the CTP.

7.5.2 (Other) Secondary endpoint(s)

Part A:

The number of patients with DLTs observed during the on-treatment period will be analysed descriptively and will be displayed by dose level.

PK endpoints will be analysed descriptively as well. Plasma (and urine) concentrations of BI 891065 will be plotted against time. The calculation of the PK parameters, as well as the descriptive and comparative analysis of the PK parameters, will be based on the methods outlined in Section 7.3.5 of the CTP, as well as in [\(9\)](#).

OR by investigator's assessment based on RECIST v1.1 will be analysed descriptively for the treated set in terms of the ORR, defined as the proportion of patients with best overall response of CR or PR.

Part B:

[figure not shown]
The number of patients with DLTs observed during the on-treatment period will be analysed descriptively and displayed by dose level.

PK endpoints will be analysed descriptively as well. Plasma concentrations of BI 891065 and of BI 754091 will be plotted against time. The calculation of the PK parameters, as well as the descriptive and comparative analysis of the PK parameters, will be based on the methods outlined in Section 7.3.5 of the CTP as well as in (9).

OR by investigator's assessment based on RECIST v1.1 will be analysed descriptively for the treated set in terms of the ORR, defined as the proportion of patients with best overall response of CR or PR.

Part C:

Duration of OR by investigator's assessment based on RECIST v1.1 will be summarised by its median and quartiles derived using the Kaplan-Meier estimation procedure. Duration of OR can only be calculated for patients in the treated set that have an OR.

7.7 EXTENT OF EXPOSURE

For all 3 trial parts, duration of BI 891065 intake will be summarised descriptively.

The number of BI 754091 courses will be assessed for Part B and Part C.

For all 3 trial parts, the number of patients with at least one dose reduction of BI 891065 will be displayed and the time to first dose reduction of BI 891065 will be analysed descriptively as well as using Kaplan-Meier methods based on the treated set. Patients who discontinue BI 891065 without a dose reduction will be censored at the date of the last BI 891065 intake for this analysis. Furthermore, dose intensity of BI 891065 will be calculated for all 3 trial parts and dose intensity of BI 754091 will be calculated for Part B and Part C.

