Figure 3.1: 1 Design of trial 1379.1 including 2 dose-escalation parts and 1 expansion cohort

Patients will continue treatment as long as they are deriving clinical benefit in the opinion of the Investigator, or until withdrawal of consent, occurrence of unacceptable toxicity, or for additional reasons detailed in Section 3.3.4.1.

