3.3.4.1 Withdrawal from trial treatment

An individual patient is to be withdrawn from trial treatment(s) if:

- The patient wants to withdraw from trial treatment, without the need to justify the decision.
- The patient needs to take concomitant drugs that interfere with the investigational product or other trial medication.

- The patient can no longer be treated with trial medication for other medical reasons (such as surgery, adverse events, other diseases, or pregnancy [see Section 5.2.6.8]).
- The patient has been non-compliant with important trial procedures and, in the opinion of both, the Investigator and Sponsor representative, is not willing or able to stick to the trial requirements in the future.
- Recurring radiologic progression. Note: In the case of initial radiological PD, patients will be allowed to stay on treatment if the following criteria are met:
 - The Investigator feels that it is in the patient’s best interest
 - The patient signed an informed consent form specific for this circumstance after acknowledging that this practice is not considered standard in the treatment of cancer. The specific informed consent process for this circumstance includes discussion of alternative treatment options, including any available approved therapies (if applicable) and participation in alternative clinical trials.
 - Absence of clinical symptoms or signs indicating clinically significant PD
 - No decline in performance status
 - Absence of rapid PD or threat to vital organs or critical anatomical sites (e.g., central nervous system metastasis, respiratory failure due to tumour compression, spinal cord compression) requiring urgent alternative medical intervention
 - No significant, unacceptable, or irreversible toxicities related to study treatment.
- A pause of treatment or delayed start of treatment of more than 12 weeks due to SAEs/AEs
- The following adverse event(s) occur:
 - Cytokine release syndrome CTCAE Version 5.0 (R18-1357) Grade 3 or 4
 - Immune related AEs requiring permanent study drug discontinuation as described in Guidelines for Management of Immune-Related AEs (Appendix 10.2):
 - Grade 3 to 4 pneumonitis
 - Grade 3 to 4 adrenal insufficiency
 - Grade 4 diabetes mellitus
 - Any grade encephalitis
 - Grade 4 hypophysitis
 - Grade 4 rash
 - Grade 3 to 4 colitis or recurrent colitis of any grade
 - Any recurrent Grade 3 to 4 AE
 - Transaminase increases >5 times ULN or total bilirubin >3 times ULN

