5.4.2 Extent of Exposure

Duration of BI 891065 intake is defined as the time from first administration of BI 891065 until the last administration of BI 891065 +1 day.

The duration of BI 754091 intake will be assessed in terms of number of BI 754091 courses administered for Part B and Part C.

The time to first dose reduction of BI 891065 is defined as the time from first administration of BI 891065 to the first administration of the first reduced dose of BI 891065 +1 day.

Dose intensity (%) will be calculated as the total dose received by the patient divided by the planned total dose, where the planned total dose will be calculated as the dose that the patient should have received between the day of first administration and the date of last administration of BI 891065 (for the dose intensity of BI 891065) and BI 754091 (for the dose intensity of BI 754091), respectively. That is, the actual dose will be divided by the amount of drug that would have been administered had the protocol-specified first dose been administered at each day according to the protocol schedule until the end of treatment.

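### Kaplan-Meier for time to first BI 891065 dose reduction censors patients who stop treatment, so its curve and quantiles overstate how many patients are reduced and how early

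*SAP*

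**What the plan says.** SAP 5.4.2 defines the variable: "The time to first dose reduction of BI 891065 is defined as the time from first administration of BI 891065 to the first administration". The interval ends when the patient first takes a lowered dose, and one day is added.

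SAP 7.7 sets the analysis: "the time to first dose reduction of BI 891065 will be analysed descriptively as well as using Kaplan-Meier methods based on the treated set". The censoring rule follows: "Patients who discontinue BI 891065 without a dose reduction will be censored at the date of the last BI 891065 intake for this analysis". The same section also plans a simple count: "the number of patients with at least one dose reduction of BI 891065 will be displayed".

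SAP 7 fixes the content of time-to-event tables: "number of patients with event [N(%)], <time to event> [months] followed by P25 (25th percentile), median, P75 (75th percentile) and number of patients censored". SAP 6.1 presents planned analyses by dose cohort and in total for Parts A and B. SAP 4 records that Part C was cancelled without enrolling anyone.

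The available text names no competing-risk method for this variable. It does not say that the target is the risk of reduction had treatment continued, and it gives no rule for patients still on treatment at data cut-off.

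**The concern.** The event needs an intake of BI 891065. Once a patient has permanently stopped, it cannot happen. Kaplan-Meier nevertheless treats a censored patient as someone who could still be reduced later at the same rate as those remaining at risk, and spreads that patient's weight over later reductions. The result is the chance of reduction in a setting where nobody stops, which is not the proportion of patients reduced.

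Stopping will not be rare. Treatment has no fixed length (Protocol 3.1: "Patients will continue treatment as long as they are deriving clinical benefit in the opinion of the Investigator"), so discontinuation is the expected end of follow-up for most patients.

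The censoring is also unlikely to be independent of the event. Protocol 3.3.4.1 lists among the reasons for withdrawal: "The patient can no longer be treated with trial medication for other medical reasons (such as surgery, adverse events, other diseases". Under Protocol 4.1.7, a non-immune Grade 3 event leads to a pause with a possible restart one dose lower, while a Grade 4 event generally leads to withdrawal. The same toxicity process can thus produce the event or the censoring. For immune-related events, Protocol 10.2 allows only interruption or permanent discontinuation.

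At stake is a tolerability display in the report that could contradict the count printed beside it.

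**Working it through.** **Plan's own figure.** There is none. The documents state no expected reduction rate, discontinuation rate or time to reduction, so every rate below is an assumption.

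**Formulas.** Let h_r and h_d be constant hazards of first reduction and of discontinuation without reduction.
- Kaplan-Meier with discontinuation censored estimates 1 − exp(−h_r·t).
- Cumulative incidence with discontinuation as competing event is h_r/(h_r + h_d) × [1 − exp(−(h_r + h_d)·t)].

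**Results at t = 6 cycles, hazards per cycle.**

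| h_r | h_d | 1-KM | Cumulative incidence |
|---|---|---|---|
| 0.02 | 0.15 | 1 − e^(−0.12) = 11.3% | (0.02/0.17)(1 − e^(−1.02)) = 7.5% |
| 0.05 | 0.15 | 1 − e^(−0.30) = 25.9% | (0.05/0.20)(1 − e^(−1.20)) = 17.5% |
| 0.05 | 0.25 | 1 − e^(−0.30) = 25.9% | (0.05/0.30)(1 − e^(−1.80)) = 13.9% |
| 0.10 | 0.25 | 1 − e^(−0.60) = 45.1% | (0.10/0.35)(1 − e^(−2.10)) = 25.1% |

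**Effect on the quantiles the SAP lists.** Assume 20% of patients are ever reduced and a median of 3 months on the initial dose. The total hazard is ln 2/3 = 0.231 per month, and h_r = 0.2 × 0.231 = 0.0462.
- At 6 months: cumulative incidence 0.2 × (1 − 0.25) = 15.0%; 1-KM = 24.2%.
- At 12 months: 0.2 × (1 − 0.0625) = 18.8%; 1-KM = 42.6%.
- Cumulative incidence never reaches 25%, so its P25 is not reached. Kaplan-Meier gives P25 = −ln(0.75)/0.0462 = 6.2 months and median = ln 2/0.0462 = 15 months, although 80% of patients are never reduced.

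With 10–30% ever reduced and medians of 2–6 months, the ratio of 1-KM to cumulative incidence is 1.25–2.15 at 6 months and 1.51–3.46 at 12 months.

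**Finite samples.** In 20,000 simulated cohorts of 30 patients (20% ever reduced, 3-month median), mean 1-KM against the actual proportion reduced was 24.2% against 15.0% at 6 months and 42.0% against 18.7% at 12 months. 1-KM was higher in 99.0% and 99.8% of cohorts and lower in none.

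**A small cohort, with no hazard assumption.** Take 6 patients, the evaluable number at 400 mg in Part A (Protocol Table 7.1.2: 2). Suppose five stop without a reduction and the sixth is reduced later. At that moment one patient is at risk, so 1-KM = 1 − (1 − 1/1) = 100%. The actual proportion is 1/6 = 17%, and the table would print a median time to reduction.

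**The case against.** The strongest reply is that the unbiased figure is already planned. The number of patients reduced stands in the same section, the event N(%) is in the table format, and both are shown by dose cohort. SAP 7.8.1 also reports adverse events leading to reduction and to permanent discontinuation. This stands: a reader might infer that dose-reduction rates by dose level come out inflated, but those counts are untouched. Only the Kaplan-Meier curve and quantiles are affected.

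A reader might also infer that the recommended dose is at risk. The documents do not support that. Dose selection rests on the BLRM with overdose control, DLTs, safety, PK and target engagement as judged by the SRC (Protocol 3.1, 4.1.3.2, 4.1.4, 4.1.8). Time to first reduction is not named there and is not a primary or secondary endpoint.

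The percentages at 6 cycles rest on assumed hazards, and the SAP lists quantiles, not probabilities at a time point. First-cycle DLTs were 0/22 in Part A and 1/19 in Part B (Protocol Tables 7.1.2: 2 and 7.1.2: 5). These are not reduction rates, but a low reduction hazard is plausible; at 0.02 against 0.15 the gap is about 4 points.

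It is tempting to add dependent censoring as a second upward bias. That does not follow. If patients who stop for toxicity were those most likely to be reduced, Kaplan-Meier would understate its own hypothetical target. The upward direction claimed here is relative to the proportion actually reduced.

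Finally, Kaplan-Meier could be defended as describing the risk of reduction while on drug. The SAP does not declare that target, and it would need independent censoring, which is doubtful when adverse events lead to either outcome.

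**Conclusion.** The point holds for the Kaplan-Meier output in Parts A and B. The direction needs no assumed rates: with permanent discontinuation as a competing event, 1-KM is never below the cumulative incidence and exceeds it once a reduction follows another patient's discontinuation. The listed quantiles, read as the times by which a quarter, half or three quarters of patients are reduced, are correspondingly too early, or are reported where they should be shown as not reached.

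The size cannot be taken from the documents. Under the constant hazards assumed above, the gap at 6 cycles runs from about 4 to 20 percentage points. The point concerns permanent discontinuation only: a paused patient may restart at a lower dose and remains at risk.

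The consequence is minor. This is a descriptive exposure summary, and no MTD, DLT or sample-size result changes.

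**What to change.** Replace the censoring sentence in SAP 7.7 so that:
- first dose reduction is summarised by cumulative incidence (Aalen-Johansen), with permanent discontinuation of BI 891065 or death without a reduction as the competing event;
- only patients still on treatment at data cut-off are censored;
- the estimate is shown in total for Part A and for Part B. By dose cohort, give the counts of patients reduced and of patients discontinued without reduction, because evaluable cohorts had only 1–6 patients in Part A and 5–8 in Part B.

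If Kaplan-Meier is kept, label it as conditional on remaining on treatment and not as the proportion of patients reduced.

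The cost is one SAP sentence and a standard SAS option, with no new data. The downside is slightly less familiar output. A low incidence of reduction must also be read next to the discontinuation counts, since a cohort whose patients stop outright for toxicity will show few reductions. This is a cheap improvement.
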